6.4.4 Virology Endpoints

The virology endpoints for this study are as follows:

- Time to cessation of viral shedding by *virus titer and by RT-PCR*
The time to cessation of viral shedding will be analyzed using *similar methods* as specified for the primary endpoint. Patients who are lost to follow-up, who do not have cessation of viral shedding, or who die will be censored at their last contact date or date of death, whichever is applicable.
- Change from baseline in influenza virus titer and in the amount of virus RNA (RT-PCR) at each timepoint
- Proportion of patients with positive influenza virus titer and proportion of patients positive by RT-PCR at each time point
- Area under the curve (AUC) over time in virus titer and amount of virus RNA (RT-PCR)

For the incidence and rate endpoints, missing data imputations will be specified in the SAP.

For incidence and rate endpoints, the difference in proportions, 95% CIs, and the p-values will be presented.

Continuous endpoints, such as change from baseline endpoints, will be analyzed using an analysis of covariance (ANCOVA) model with region (North America, EMEA, ROW), NEWS2 (≤ 7 , > 7), and time from symptom onset to study treatment (≤ 48 hours, > 48 hours) as stratification variables, and the baseline value of the studied measure as a covariate.

The additional virology endpoints are as follows:

- Polymorphic and treatment-emergent amino acid substitutions in the *PA*, *PB1*, *PB2*, and *NA* genes
- Drug susceptibility in patients with evaluable virus

The additional virology endpoints will be summarized descriptively. Further details will be described in a resistance analysis plan.

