Proportion of patients positive by RT-PCR will be presented by treatment at each visit is defined as the percentage of patients with detectable virus RNA (2.05 for flu A and 2.83 for flu B log₁₀ virus particles/mL) among those assessed by RT-PCR on Days 2, 3, 4, 5, 7, and 10. The Cochran-Mantel-Haenszel test with region (North America, EMEA, ROW), NEWS2 at baseline (≤ 7 , > 7), and time from symptom onset to study treatment (≤ 48 hours, > 48 hours) as stratification variables, and the baseline value as a covariate will be used to compare proportion of patients positive by RT-PCR between treatments at each scheduled time point.

Patients with a positive by RT-PCR on Day 1 will be included in this analysis.

Area under the curve in virus titer

Area under the curve (AUC) in virus titer will be presented by treatment group and will be calculated using the trapezoidal method. AUC of change from time 0 (t_0) to time K (t_k) is given by the formula:

$$\sum_{k=1}^K \frac{(y_k + y_{k-1})(t_k - t_{k-1})}{2}$$

where t_k (hours) represents the date of the k th viral titer assessment ($k = 0, \dots, K$) and y_k represents the log₁₀ value of the k th viral titer assessment (TCID₅₀/mL). 24-hours of time will be converted into one day. Patients with a positive virus titer on Day 1 will be subjected to this analysis. The lower limit of quantification and lower limit of detection is defined as 0.75 log₁₀ TCID₅₀/mL for flu A and 0.75 log₁₀ TCID₅₀/mL for flu B (TCID₅₀/mL). If a patient is infected with multiple virus types, the sum of those virus titers will be used for analysis.

Additionally, the AUC in virus titer adjusted for baseline will be presented by treatment group and be calculated using the trapezoidal method. AUC of change from time 0 (t_0) to time K (t_k) adjusted for baseline is given by the formula:

$$\sum_{k=1}^K \frac{(y_k + y_{k-1} - 2y_0)(t_k - t_{k-1})}{2}$$

where t_k (hours) represents the date of the k^{th} viral titer assessment ($k = 0, \dots, K$) and y_k represents the \log_{10} value of the k^{th} viral titer assessment (TCID₅₀/mL). 24-hours of time will be converted into one day. Patients with a positive virus titer on Day 1 will be subjected to this analysis. The lower limit of quantification and lower limit of detection is defined as $0.75 \log_{10}$ TCID₅₀/mL for flu A and $0.75 \log_{10}$ TCID₅₀/mL for flu B (TCID₅₀/mL). If a patient is infected with multiple virus types, the sum of those virus titers will be used for analysis.

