Area under the curve in the amount of virus RNA (RT-PCR)

AUC in virus RNA (RT-PCR) will be presented by treatment group and is defined as AUC of change from baseline in the amount of virus RNA (RT-PCR) from Day 1 to Day 10. AUC is calculated using the trapezoidal method similar to AUC in virus titer.

Patients with a positive RT-PCR result on Day 1 will be subjected to this analysis. The lower limit of quantification is defined as 2.18 for flu A and 2.93 for flu B (\log_{10} virus particles/mL). If a patient is infected with multiple virus types, the sum of those the amount of virus RNA will be used for analysis.

Exposure and virology will be included in the pop PK report.

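### SAP 4.6 names no analysis model for viral AUC, although Protocol 6.4.4 sets baseline-adjusted ANCOVA for continuous virology endpoints, and SAP 3.3 does not list the difference

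*SAP*

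**What the plan says.** Protocol 6.4.4 lists AUC in virus titre and in virus RNA among the virology endpoints. Its method sentence reads "Continuous endpoints, such as change from baseline endpoints, will be analyzed using an analysis of covariance (ANCOVA) model with region", with baseline NEWS2 and time from symptom onset as the other factors, "and the baseline value of the studied measure as a covariate". Change from baseline is given there as an example of a continuous endpoint, and AUC is continuous too.

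SAP 4.6 treats the endpoints as follows.

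- Change from baseline in titre and in RNA: ANCOVA with the three factors and the baseline value, as in the protocol.
- Titre AUC: "in virus titer will be presented by treatment group and will be calculated using the trapezoidal method". A second version follows: "Additionally, the AUC in virus titer adjusted for baseline will be presented by treatment group". Its formula subtracts the baseline value at every time.
- RNA AUC: it "will be presented by treatment group and is defined as AUC of change from baseline". No raw version is planned.

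No model, test or covariate is named for any AUC. SAP 3.3 records two changes since Protocol v2.0, the interim futility statistic and the clinical response definition. AUC is not among them.

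**The concern.** Virological activity, compared between arms, is a stated objective, and AUC is one of its named endpoints. Randomisation (Protocol 4.2) is stratified by region, NEWS2 and onset time, not by viral load, and the AUC analyses include only patients positive on Day 1. Some chance imbalance in baseline viral load is therefore likely. Raw AUC carries it into the comparison in one direction. Baseline-subtracted AUC can carry it in the other, because a patient with a high baseline has further to fall before reaching the floor. RNA AUC is planned only in the subtracted form.

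At stake are the precision of the antiviral comparison and the fact that, with no model named, the choice between raw, subtracted and adjusted AUC stays open until data are seen.

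**Working it through.** **The plan's own figures.** The documents state no power, SD or baseline correlation for any virology endpoint, so there is nothing to reproduce on this point. The sample size (264 patients, at least 80% power) concerns time to clinical improvement. It reproduces (80.2% with 264 events, hazard ratio 63/94 and the futility look) but says nothing about AUC.

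**Relation between the two AUCs.** With swabs on Days 1, 2, 3, 4, 5, 7 and 10 (SAP 4.6) and none missing, the period is T = 10 − 1 = 9 days. The second SAP formula then reduces to

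subtracted AUC = raw AUC − 9 × baseline.

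This is a full correction only if raw AUC rises by 9 units for each log10 of baseline.

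**Why that over-corrects.** Take assumed baselines one SD either side of 4.3 (SD 1.6), a decline of 0.9 log10 per day, and 0.749 once below quantification. (The SAP gives that value under change from baseline; I assume it applies here.)

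- Baseline 2.7: titres 2.7, 1.8, 0.9, then 0.749. Raw AUC = 2.25 + 1.35 + 0.8245 + 0.749 + 1.498 + 2.247 = 8.92. Subtracted = 8.92 − 24.3 = −15.38.
- Baseline 5.9: titres 5.9, 5.0, 4.1, 3.2, 2.3, 0.749, 0.749. Raw AUC = 5.45 + 4.55 + 3.65 + 2.75 + 3.049 + 2.247 = 21.70. Subtracted = 21.70 − 53.1 = −31.40.

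Both patients clear virus at the same rate. Raw AUC differs by 12.78, which is 12.78/3.2 = 4.0 per log10 of baseline. Subtracted AUC differs by −16.02, or −5.0 per log10, since 4.0 − 9 = −5.0. Neither version removes baseline. ANCOVA estimates the slope instead of fixing it at 0 or 9.

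**Variances.** Let rho be the correlation of raw AUC with baseline, and r = 9 × SD(baseline)/SD(raw AUC). With the variance of raw AUC set to 1:

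- subtracted: 1 + r² − 2·rho·r
- ANCOVA: 1 − rho²

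The excess over ANCOVA is rho² for raw AUC and (r − rho)² for subtracted AUC. Neither can be negative. The share of precision lost is 1 − Var(ANCOVA)/Var(alternative).

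| rho | lost vs raw | lost vs subtracted, r = 1 | r = 1.5 | r = 2 |
|---|---|---|---|---|
| 0.3 | 9% | 35% | 61% | 76% |
| 0.5 | 25% | 25% | 57% | 75% |
| 0.7 | 49% | 15% | 56% | 77% |
| 0.8 | 64% | 10% | 58% | 80% |

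Against raw AUC the loss passes one half only when rho exceeds 0.707.

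**Plausible rho and r, for titre.** All inputs here are assumed.

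- Mean baseline 4, decline 0.8 log10/day, baseline SD 1.0–1.5, slope SD 0.1–0.5, noise SD 0.5–1.0, planned swab days and floor: rho 0.41–0.90 and r 1.1–2.5. Losses are 17–80% against raw and 34–86% against subtracted.
- Check of one cell (rho 0.76, r 1.58): ANCOVA 1 − 0.578 = 0.422; subtracted 1 + 2.496 − 2.402 = 1.095. Ratios to ANCOVA: raw 1/0.422 = 2.4, subtracted 1.095/0.422 = 2.6.
- Baseline SD 1.0–1.6, slope SD 0.2–0.5, noise SD 0.5–1.0: variance relative to ANCOVA 1.2–3.6 times for raw and about 1.6–7 times for subtracted.
- A wider grid (baseline SD 0.8–1.6, slope SD 0–0.6) stretches the losses to 6–84% and 28–93%.

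The ends of these ranges reflect the grid chosen; they are not bounds.

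**The case against.** The strongest reply is that the SAP is silent on AUC and does not substitute another method, so the protocol's ANCOVA still governs. Presentation by group does not exclude a model either: SAP 4.6 says much the same of the proportion endpoints and then names a Cochran-Mantel-Haenszel test. That is fair, but for AUC no test follows, and the SAP is where the method should be settled.

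AUC also lies outside the testing hierarchy and has no stated power. Randomisation makes the problem noise, not systematic bias. For titre, showing raw and subtracted AUC together would tend to expose an imbalance, because it can move them in opposite directions. All of this stands and limits the consequence. The last part does not help RNA, where only the subtracted form is planned.

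Three stronger readings are tempting and not supported.

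- A reader might infer that the SAP abandons ANCOVA for virology generally. It keeps it for both change-from-baseline endpoints.
- A reader might infer that baseline adjustment was also dropped for time to cessation of shedding. The protocol says "The time to cessation of viral shedding will be analyzed using" methods similar to the primary endpoint, and the SAP agrees. Baseline viral load is in neither, so nothing was removed.
- A reader might infer that most of the available precision is lost. That depends on rho and r, which the documents do not give; at rho 0.5 the loss against raw AUC is 25%.

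**Conclusion.** The point holds for AUC only. The protocol's method for continuous virology endpoints is not carried into the SAP for titre or RNA AUC, and the difference is not declared. Baseline-adjusted ANCOVA is at least as precise as either planned summary in large samples, whatever the inputs.

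The size rests on assumptions: about 1.2 to 3.6 times the ANCOVA variance for raw AUC and about 1.6 to 7 times for subtracted AUC. These assume linear decline to the floor, complete swabs and the SDs listed above. They were worked out for titre; RNA has different quantification limits and was not simulated. No power figure for AUC should be quoted as a property of this trial. The primary analysis and the hierarchy are untouched. The change is worth making because it is nearly free and restores agreement with the protocol.

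**What to change.** In SAP 4.6, state that arms are compared on titre AUC and on RNA AUC, with raw AUC as the response, by the ANCOVA already specified for change from baseline: region, NEWS2, onset time and baseline log10 value. Report the adjusted difference with its 95% CI. Derive a raw RNA AUC for this purpose. Keep baseline-subtracted AUC as description only. Nothing is lost by this: where T is the same for all patients, subtracted AUC differs from raw AUC by a fixed multiple of a covariate already in the model, so the adjusted treatment difference is identical.

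If AUC is meant to stay descriptive, list that in SAP 3.3 as a departure from Protocol 6.4.4.

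A Cox model for time to cessation with baseline log10 viral load as a covariate may be added as a supplementary analysis. It is optional and corrects nothing.

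The cost is SAP wording and a small amount of programming. All values are already collected.

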4.6.1 Exploratory Endpoints

Polymorphic and treatment-emergent amino acid substitutions in the PA, PB1, PB2, and NA genes

Sanger sequencing of PA and NA will be performed for all or neuraminidase treated patients, respectively, and with paired (pre and post dose) samples available, at baseline and at the last evaluable timepoint (last sample with $> 4 \log_{10}$ viral particles/ml). For patients with amino acid substitutions in the PA gene, additional sequencing will be performed for all earlier timepoint samples to evaluate the timepoint of emergence of the amino acid substitution. In addition, sequencing of PB1 and PB2 genes will be performed on samples selected based on the criteria below. The number and proportion of patients with the detected amino acid substitutions will be reported for all investigated genes.

Sequencing of PB1 and PB2 will be done for:

- baseline viruses with reduced susceptibility to baloxavir (fold-change in $EC_{50} > 10$ for type A viruses and > 5 for type B viruses compared to reference virus in phenotypic assay).
- viruses (baseline and last evaluable time-point) without amino acid substitution in PA, but with reduced response to treatment or with virus rebound.

These will be defined according to the following criteria below in [Table 13](#). If an amino acid substitution is detected, an additional intermediate time point sample will be sequenced.

Table 13 PB1 and PB2 Sequencing

	Criteria
1) Subjects who exhibit viral titer rebound:	Viral titer at [(a certain time point) – (just before time point)] \geq 2 x SD value of viral titer of control virus in assay * * [REDACTED]
2) Subjects who continue to shed virus at Day 6 and beyond:	Viral titer (log ₁₀ TCID ₅₀ /mL) at Day 6 and beyond > 1.5
3) Subjects who do not show a reduction in virus titer:	Viral titer (log ₁₀ TCID ₅₀ /mL) at a certain time point: A > 1.5 Viral titer (log ₁₀ TCID ₅₀ /mL) at just before time point: B > 1.5 AND Viral titer (log ₁₀ TCID ₅₀ /mL) at [(a certain time point: A) - (just before time point: B)] \geq 0

Drug susceptibility in patients with evaluable virus

As assessments of the drug susceptibility of the influenza virus, the 50% effective concentration (EC₅₀) of baloxavir or the 50% inhibitory concentration (IC₅₀) of neuraminidase inhibitor # (will be measured by the ViroSpot™ or NA-Star® assay, respectively, using baseline swab samples.

#The neuraminidase inhibitor (oseltamivir acid or zanamivir or peramivir) selected for drug susceptibility testing in the NA-Star® assay will be based on the neuraminidase inhibitor received by the patient on study Day 1

Values (EC₅₀ or IC₅₀) will be compared with values of reference strains and respective ratio (EC₅₀ / EC₅₀ reference or IC₅₀ / IC₅₀ reference) will be reported.

The following influenza virus vaccine strains from 2018-2019 season will be used as reference for the ViroSpot™ assay: A/Michigan/45/2015 (H1N1)pdm09 for A/H1N1 samples, A/Singapore/INFIMH-16-0019/2016 for A/H3N2 samples from Northern hemisphere, A/Switzerland/8060/2017 for A/H3N2 samples from Southern hemisphere, and B/Colorado/06/2017-like virus (B/Victoria/2/87 lineage) and B/Phuket/3073/2013-like virus (B/Yamagata/16/88 lineage) for influenza type B samples. Mean EC₅₀ value of the two B reference strain EC₅₀ values will be used to calculate EC₅₀ ratio.

Reference viruses used for the NA-Star® assay are A/Puerto Rico/8/34 (H1N1) and B/Lee/1940.

Respiratory coinfections (Biofire)

All baseline samples will be tested for respiratory pathogens using the qualitative PCR-based FDA cleared BioFire FilmArray® Respiratory Panel 2 assay. This assay detects 17 respiratory viral or bacterial pathogens in addition to influenza A and B. Frequency and proportions for each co-infection will be presented.

Influenza antibody titer

A hemagglutination inhibition assay for the detection of influenza virus A and B specific antibodies will be performed from blood samples at baseline and at end of the study and the antibody titer will be determined. The lower limit of quantification is defined as a hemagglutination inhibition titer of 10. Summaries of findings will be presented.

4.6.2 Subgroup Analyses

Subgroup analysis of the following virology endpoints, based on virus type and subtype, will be conducted by treatment group:

- Time to cessation of viral shedding by RT-PCR
- Time to cessation of viral shedding by virus titer

For the baloxavir treatment group only, an additional subgroup analysis comparing the patients with or without the presence of virus with an I38x substitution will be conducted for the following:

- Time to cessation of viral shedding by RT-PCR
- Time to cessation of viral shedding by virus titer
- Number and % of patients having 2 doses of baloxavir; number of patients having 3 doses of baloxavir

Subgroup analyses will be produced where appropriate and where the number of patients in each subgroup is sufficient.

4.7 SAFETY ANALYSES

The safety analysis population will be used for all safety analyses. Patients will be analyzed according to the treatment they actually received.

4.7.1 Adverse Events

AEs will be classified by system organ class and preferred term using the latest version of Medical Dictionary for Regulatory Activities (MedDRA) and adverse event severity will be graded according to National Cancer Institute Common Terminology Criteria for Adverse Events (NCI CTCAE) v5.0. Of reported AEs on the eCRF, AEs reported after the initial dose of study drug will be used for safety analyses.

In summaries by SOC and PT, AEs will be sorted by overall decreasing frequency within each SOC and PT.

All Adverse Events

Only treatment-emergent AEs will be summarized. Treatment-emergent events are defined as those AEs with observed or imputed onset date on or after the start date of trial treatment. Only where the most extreme intensity is greater than the initial intensity (or if most extreme intensity is not missing and initial intensity is missing) will events with an onset date prior to the start of study treatment be considered treatment-emergent. An AE with a completely missing start date will be assumed to be treatment-emergent unless the AE has a complete non-imputed end date that is prior to study day 1.

All Adverse events will be coded and tabulated by system organ class and/or preferred term. In tabulations, preferred terms and their associated system organ class will be presented in order of descending frequency summed across the treatment arms. Adverse events will also be tabulated by severity and relationship to study medication as indicated by the investigator.

The following will also be summarized by treatment arm and listings produced where required:

- Serious AEs
- AEs leading to withdrawal from study
- AEs leading to death
- AEs leading to a withdrawal of study drug
- AEs occurring in $\geq 5\%$ of patients in at least one treatment group
- AEs occurring in $\geq 1\%$ of patients in at least one treatment group
- AEs by background NAI treatment
- AEs by outcome
- AEs by time of onset
- AEs by CTCAE Grade
- AE related to Study Medication or SOC NAI
- AE related to Study Medication

Adverse Events of Special Interest

All adverse events of special interest (AESI) will be presented by treatment group. AESI include but are not limited to the following:

- Case of an elevated ALT or AST in combination with either an elevated bilirubin or clinical jaundice, as defined in protocol
- Suspected transmission of an infectious agent by the study drug

Adverse Events by Dosage

Overall summary of adverse event will be presented by baloxavir dosage (2 dose, 3 dose)

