4.3.2.1 Baloxavir Marboxil and Matching Placebo (Study treatment)

Baloxavir marboxil or matching placebo will be administered orally according to body weight (40 mg for patients weighing 40 to <80 kg; 80 mg for patients weighing \geq 80 kg) either in tablet form (20-mg tablets) or granules for oral suspension for patients unable to swallow or with a nasogastric tube in situ (e.g., in intubated patients).

Dosing will occur on Day 1 and Day 4, with a further dose at Day 7 for patients who have not improved according to *at least 1 of the following* specific criteria at Day 5:

- Ongoing mechanical ventilation
- Persistent fever
- Severely immunocompromised
- *Pneumonia*
- *Confirmed*/suspected influenza-related complication

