2. STUDY DESIGN

2.1 DESCRIPTION OF THE STUDY

Study CP40617 is a Phase III, randomized, double-blind, placebo-controlled, multicenter study to assess the efficacy, safety, and PK of baloxavir marboxil in combination with a standard-of-care (SOC) neuraminidase inhibitor (NAI) (i.e., oseltamivir, zanamivir, or peramivir), compared with a matching placebo in combination with a SOC NAI in approximately 366 hospitalized adults and adolescent patients (aged ≥ 12 years) with influenza.

Patients will be randomized in a 2:1 ratio to receive baloxavir marboxil or matching placebo. Study treatment must be given in combination with a SOC NAI according to investigator preference (i.e., oseltamivir, zanamivir, or peramivir).

[figure not shown]
The study consists of two periods: a 10-day treatment period and a 25-day follow-up period. Therefore, the maximum study duration for each patient will be 35 days.

This study will be conducted at approximately 250 global sites in both Northern and Southern hemispheres.

An external independent Data Monitoring Committee (iDMC) will evaluate safety according to policies and procedures detailed in an iDMC Charter. Additionally, the iDMC will review the primary efficacy data for futility at time of interim analysis.

[Figure 1](#) presents an overview of the study design. A schedule of activities is provided in [Appendix 2](#) .

Figure 1 Study Schema

NAI=neuraminidase inhibitor; SOC=standard-of-care.

- ^a All patients will receive at least two doses of baloxavir marboxil or its matching placebo (i.e., Days 1 and 4). A third dose may also be administered on Day 7 if clinical improvement is not observed at Day 5 according to protocol defined criteria.
- ^b A SOC NAI should be administered to cover a minimum of treatment exposure from Day 1 to Day 5. This treatment may be extended to Day 10 or beyond, at the discretion of the investigator and in accordance with local clinical practice.

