3. STUDY CONDUCT

3.1 RANDOMIZATION, STRATIFICATION AND BLINDING

Following completion of screening and after all patient eligibility requirements are confirmed, patients will undergo randomization in a 2:1 ratio stratified by three regions (i.e., North America; Europe, Middle East, and Africa [EMEA]; and rest of world [ROW]), NEWS2 score (≤ 7 , > 7), and time from symptom onset to study treatment (≤ 48 hours, > 48 hours).

All patients will receive either baloxavir marboxil or its matching placebo. A permuted-block randomization method will be used to obtain an approximate 2:1 ratio between the active treatment group and the placebo group within each stratum. The placebo and active kits are filled and packaged to look identical.

Patients, investigators, and the Sponsor will be blinded to treatment assignment.

At study completion, stratification variables recorded in the Interactive Voice/Web Response System (IxRS) will be compared to the stratification variables recorded on the electronic Case Report Form (eCRF) to identify any mis-stratifications. These will be listed for all patients. If it is found that $> 10\%$ of mis-stratifications occurred, a sensitivity analysis will be carried out on the primary endpoint, using the eCRF stratification variables in the model.

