4.7.3 Laboratory Data

All laboratory data will be converted to SI units. The International Standard for the Handling and Reporting of Laboratory Data COG 3007 (Version 4.0) will be used to implement reference ranges and marked abnormalities for laboratory data where possible.

For each of the haematological and biochemical test parameters, summary statistics of observed and change from baseline values at Day 10 will be presented by treatment group. Baseline is defined as the last assessment prior to treatment on Day 1.

A listing will present all lab assessments data for patients who had any significant change from baseline.

Summaries of the number of patients by CTC grade at each assessment will also be presented. For laboratory parameters, observations on Day 1 will be classed as baseline.

Additionally, summary statistics of observed and change from baseline values of liver function tests (Total Bilirubin, Alkaline phosphatase [ALP], Alanine aminotransferase [ALT] and aspartate aminotransferase [AST]), which are collected on Day 1, Day 4, Day 7 (if 3rd dose of baloxavir received) and Day 10, will be presented by treatment group for each scheduled time point, as well as box and whisker plots at each time point.

The number and proportion of patients who meet the pre-specified criteria shown in [Table 14](#) will be presented by treatment group during the study.

Table 14 Pre-specified Abnormal Laboratory Criteria

AST (U/L) or ALT (U/L) and Total bilirubin (mg/dL)
AST(U/L) or ALT (U/L) > 3 × ULN
AST(U/L) or ALT (U/L) > 5 × ULN
AST (U/L) or ALT (U/L) > 3 × ULN and Total bilirubin (mg/dL) > 2 × ULN

ALT= Alanine aminotransferase; AST= aspartate aminotransferase; ULN = upper limit of normal.

A listing of all pregnancies will be presented.

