- u. Study treatment dosing will occur on Day 1 and Day 4, with a further dose at Day 7 for patients who have not improved at Day 5. Specific criteria must be met for additional dosing at Day 7 include ongoing mechanical ventilation, persistence of fever, severely immunocompromised, confirmed/suspected influenza-related complication, or pneumonia. Study treatment will be given in the hospital setting due to the requirement for pre-dose liver function monitoring. In order to maximize the study blind, it is mandated that each site delegates the preparation of baloxavir marboxil and placebo granules to dedicated site personnel that are not involved in any other study related assessments or procedures. Dose administration cannot be conducted by a mobile nurse.
- v. The SOC NAI should to be administered to cover the minimum treatment exposure from Day 1 through Day 5, where possible. This may be extended to Day 10 or beyond, at the discretion of the investigator and in accordance with clinical practice (see Protocol Section 4.3.2.2 for further guidance).
- w. The time of last food intake prior to dosing with study treatment and the fasting period following study treatment should be recorded on Days 1 and 4, as well as on Day 7 if additional study treatment is administered.
- x. Sparse PK samples: See Protocol Appendix 3.
- y. Sequential PK samples: See Protocol Appendix 3. Although sequential PK sampling is optional the protocol aim is to attempt to collect it from a maximum of 12 patients.
- z. Palatability and acceptability assessments are to be conducted for patients that take study treatment as an oral suspension, and are awake and compos mentis during administration on Day 1 and Day 4 (as well as Day 7 if an additional dose is required). The time of assessment should be completed approximately 1 minute after swallowing the drug solution, and before rinsing the mouth.
- aa. Bodyweight measurement in the 'Follow-Up Period: Discharged D11-30' column was a medical editing error. Bodyweight is only measured at Screening and not at any other timepoint during the study.

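### The adverse-event summary by number of doses names only baloxavir columns, so its 2-dose v 3-dose contrast mixes any dose effect with the reasons for giving a third dose

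*SAP*

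**What the plan says.** SAP 4.7.1, under the sub-heading on adverse events by dosage, consists of one sentence: "Overall summary of adverse event will be presented by baloxavir dosage (2 dose, 3 dose". No placebo columns are named, and there is no category for patients who received a single dose.

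The other adverse-event outputs in SAP 4.7.1 ignore dose count: "The following will also be summarized by treatment arm and listings produced where required". Protocol 6.5 contains no summary by number of doses.

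Dosing is on Days 1 and 4, "with a further dose at Day 7 for patients who have not improved" (Protocol 4.3.2.1). The triggers at Day 5 are "ongoing mechanical ventilation, persistence of fever, severely immunocompromised, confirmed/suspected influenza-related complication, or pneumonia" (SAP Appendix 2, note u). The rule covers both arms: "All patients will receive at least two doses of baloxavir marboxil or its matching placebo" (SAP 2.1, Figure 1 note), with a third possible on the same terms. The decision is blinded: "Patients, investigators, and the Sponsor will be blinded to treatment assignment" (SAP 3.1).

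**The concern.** Dose count is an outcome of the first five days as well as a measure of exposure. A patient reaches three doses because of ventilation, fever, pneumonia, another complication or severe immunocompromise. All but the last mark illness that has not resolved; the last is host risk. Each can change the adverse-event rate without any contribution from the drug.

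A table with only two baloxavir columns invites the reader to credit the difference to the third dose. The question is of interest here. Protocol 3.3.1 expects higher exposure after repeated dosing, and Protocol 6.1 counts a larger safety population for the multiple-dose regimen as a benefit of the larger sample. The table could suggest a dose-related signal that does not exist, or hide one that does. Patients who met the same criteria on placebo are in the database and would show what the background difference looks like.

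**Working it through.** **1. Denominators.** The dose-count sentence gives no figure of its own, so the starting point is the sample size in SAP 2.4. With 264 mITTI patients, 75% RT-PCR positive and 4% dropout, N = 264 / (0.75 × 0.96) = 366.7, which reproduces the stated 366 or so. The safety population does not require a positive RT-PCR, so up to 366 patients enter: 366 × 2/3 = 244 baloxavir and 366 / 3 = 122 placebo.

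**2. What the planned contrast estimates.** Let p2 and p3 be the event rates that patients with two and three doses would have without any drug effect. The 3-dose minus 2-dose difference within baloxavir equals any dose effect plus (p3 − p2). The same subtraction in placebo gives (p3 − p2) alone, provided that the two arms select similar patients for the third dose.

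**3. Three ways the documents make p3 differ from p2.**
- *Selection on illness and host risk*, from the Day 5 criteria.
- *Trigger counted as event.* Protocol 6.4.3 and SAP 4.5.3 treat influenza complications, including pneumonia, as adverse events when they arise after treatment starts, and SAP 4.7.1 counts events from the first dose. A complication arising before Day 5 can therefore cause the third dose and also appear in the 3-dose column, although it came first.
- *Longer window.* Protocol 5.3.1 collects events until 28 days after the final dose: Day 4 + 28 = 32 after two doses, Day 7 + 28 = 35 after three. That is nominally 3 days more, or 35 / 32 = 1.09.

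**4. Selection the other way.** A third dose requires being alive on Day 7, still on treatment and with acceptable liver tests (Protocol 4.5.8, 4.6.1 and Appendix 4). Fatal and treatment-stopping events before then fall among patients with one or two doses. So p3 − p2 may have either sign.

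**5. Illustrative size.** The documents give neither the share receiving a third dose nor event rates. Assume that everyone receives at least two doses, that the third-dose share is 20%, 35% or 50%, that p2 = 40% and p3 = 60% in both arms, and that there is no drug effect. The baloxavir-only table then shows 60 − 40 = 20 points. With placebo columns, both the 3-dose baloxavir minus 3-dose placebo difference and the difference in differences have expectation 0. For numbers b (baloxavir) and c (placebo), the 95% half-widths are:

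- 3 v 3 doses: 1.96 × √[p3(1 − p3)(1/b3 + 1/c3)]. At a 20% share this is 1.96 × √[0.24 × (1/49 + 1/24)] = 0.239.
- Difference in differences: add p2(1 − p2)(1/b2 + 1/c2) under the root. At a 20% share this is 1.96 × √[0.0149 + 0.0037] = 0.267.

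| Third-dose share | 3-dose n (bal / pbo) | 2-dose n (bal / pbo) | Half-width, 3 v 3 | Half-width, diff. in diff. |
|---|---|---|---|---|
| 20% | 49 / 24 | 195 / 98 | 24 points | 27 points |
| 35% | 85 / 43 | 159 / 79 | 18 points | 22 points |
| 50% | 122 / 61 | 122 / 61 | 15 points | 21 points |

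**6. How visible a spurious gap would be.** Suppose a reader tested the within-baloxavir contrast, which the SAP does not plan. Over the same three shares, the chance of nominal p < 0.05 with no drug effect is 25–35% for 40% v 50%, 72–88% for 40% v 60%, and 97–99.8% for 30% v 60%. The formula is Φ[(|p3 − p2| − 1.96 s0) / s1], with s0 the pooled and s1 the unpooled standard error. At a 20% share and 40% v 60%: Φ[(0.20 − 1.96 × 0.0793) / 0.0783] = 0.72. With 4% fewer patients dosed, these figures fall by less than 2 points.

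**The case against.** **The wording may be loose.** SAP 4.7.3 describes liver tests on "Day 7 (if 3rd dose of baloxavir received) and Day 10, will be presented by treatment group for each scheduled time point", so there the name of the drug must cover matching placebo as well. Where the SAP wants one arm only, as in the resistance subgroup of 4.6.2, it says so. The sponsor may intend both arms in the dose-count table too. This stands as a reason to say that no placebo column is named, rather than that placebo is excluded. It does not put the columns in the plan.

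**Other outputs help.** SAP 4.7.1 lists adverse events by time of onset, by arm, which gives randomised evidence on late events. SAP 4.7.3 gives Day 7 liver tests by arm. SAP 4.7.6 reports missed or incorrect doses by arm and lists patients who did not receive the expected dose, which partly covers one-dose patients. None of these tabulates adverse events by dose count in both arms.

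**Placebo is not a clean comparator.** If baloxavir changes improvement by Day 5, its third-dose patients are a different subset from those on placebo. This stands: placebo columns reduce the confounding but do not remove it, and the cells are small.

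**Stronger readings to avoid.** A reader might infer that the 3-dose column will almost certainly show more events; the opposing selection in step 4 leaves the direction open. A reader might infer that a dose signal cannot be separated from severity at all; that describes the table as worded, since the data for a better-controlled comparison are collected. A reader might also infer that the trial set out to compare three doses with two; no objective in Protocol Section 2 does so.

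**Conclusion.** The point holds as a small improvement to one supplementary descriptive table. As worded, the 2-dose v 3-dose summary within baloxavir confounds any dose effect with severity, host risk, complications that preceded the third dose, and a slightly longer reporting window. The sign of the net distortion is not known.

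Its size cannot be derived from the documents. The 20-point example and the half-widths of 15 to 24 points rest on assumed event rates and third-dose shares, and the former simply returns the gap that was assumed.

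This is not an error in the randomised safety comparison. The by-arm adverse-event tables are untouched, and no test or claim depends on the dose-count table. The risk is misreading.

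**What to change.** Reword the dose-count sentence in SAP 4.7.1 so that:

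- the overall adverse-event summary is shown for both arms side by side by number of doses received (1, 2 and 3 of baloxavir; 1, 2 and 3 of placebo), descriptively and without tests;
- events with onset on or after the Day 7 dose are shown separately, so that complications which triggered the dose are not read as its consequence;
- a footnote states that dose count is set after randomisation, so contrasts between arms within a dose count are not randomised comparisons.

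If the sponsor already intends both arms, a clarifying sentence settles the placebo columns. The change uses data already collected and affects neither the sample size nor any hypothesis test. The cost is a few extra columns, some of them with small and imprecise cells, the one-dose columns probably most of all.
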